3.2 Participant eligibility criteria

3.2.1 Inclusion criteria

Participants must meet the following criteria to be eligible for this study:

1. Able and willing to provide written informed consent and to comply with the study protocol
2. Either male or female (biological sex)
3. Aged 45-64 years (inclusive)
4. Any ancestry or background
5. Eligible for NHS health check using QRISK®2 assessment

3.2.2 Exclusion criteria

Participants who meet any of the following exclusion criteria will not be eligible for this study.

1. Those excluded from NHS health checks
2. Currently prescribed and taking statins, for any indication.

The same inclusion and exclusion criteria are applied for the provision of saliva samples. To participate in an interview, the participant must have completed the online questionnaire at visit 3.

3.3 Study Duration

The recruitment period will be 30 weeks. The duration of participant involvement will be between approximately 14 and 20 weeks, from consent to completion to the final interview (if selected).

It is expected that the study will take approx 10 months to complete.

3.4 Sample Size

The aim of this study is to demonstrate that predictive genetic testing can be incorporated into primary health care. This study is adding genetic testing to a tool that is already available; QRISK®2 predicts the likelihood of developing CVD over the next 10 years by assessing clinical data. It is intended that the addition of a genetic component to the test should not complicate the process, maintaining ease of use.

To this end it is planned to select sites of different size, capacity and resource to test assimilation of the genetic component into their varying processes. Additionally, the addition of the genetic component should not hinder the number of assessments normally undertaken, therefore high throughput is essential.

Also of interest to the study is a diverse population. The study will aim to recruit an equal number of male and female, even numbers across the 5 year age brackets (e.g., 45-49 years), and also aim to include 10-15% black, asian and minority ethnic (BAME) participants.

It is considered that 8-10 sites from areas of varying affluence and deprivation, and recruiting a high number of participants reflective of normal practice (around 100) will serve to answer the study objectives. It is planned to recruit around 1000 participants from 8-10 sites. All participants will be invited to complete an online survey. Of the participants who complete the survey a subset of 20-30 participants will be invited to take part in a telephone interview.

Approximately 30 HCPs involved in delivering the study will be invited to complete a questionnaire and take part in a focus group.

Approximately 5 representatives of the PCCs will be invited to take part in a focus group.

3.5 Randomization and Blinding

Not Applicable.

3.6 Study Assessment Schedule

The time and events schedule for the study is presented in Table 1.

| Procedures | Visit 1, Baseline | Visit 2, Results | 'Visit 3', Online Questionnaire | 'Visit 4', Phone Interview | Focus groups |
|--|----------------------|---------------------|---------------------------------------|---------------------------------|--------------------------|
| | Day 1 | + 5-12 weeks | + 0-14 days after V2 | up to 2 months after Visit 2 | Study End |
| Informed consent ¹ | X | | | | |
| Demographics | X | | | | |
| Inclusion/ Exclusion Criteria | X | | | | |
| Blood sample ² | X | | | | |
| Saliva sample ³ | X | | | | |
| QRISK®2 score ⁴ | X | | | | |
| CVD IRT Results availability ⁴ | | X | | | |
| Adverse Events ⁵ | X | X | X | X ⁶ | X ⁶ |
| Device deficiencies | X | X | | | |
| Participant Questionnaire | X (V1eDC) | | X (V3PartQ) | | |
| Interview consent | X | | | | |
| Participant Interview ⁷ | | | | X | |
| HCP Questionnaire | | X (V2eDC) | | | X ⁸ (HCPQ) |
| HCP Focus Group(s) | | | | | X ⁹ |
| NHS PCC Focus Group | | | | | X ¹⁰ |

Table 1: Schedule of assessments; patient participant, HCP and PCC.

Footnotes to Table 1 Schedule of Study Assessments

1. Signed, written informed consent obtained prior to any study specific procedure. Separate consent required for saliva samples.

2. 2x2.5ml samples for genetic analysis, the second sample as back-up in case of failure at any stage of processing.
3. A subset of participants (~100) at selected sites (1-3 sites depending on recruitment) will provide a 2ml saliva sample.
4. The QRISK®2 score will be available some days after Visit 1. The CVD IRT score will be available up to 12 weeks after the sample collection.
5. Related adverse events (ADEs) are to be collected from the provision of written informed consent up to the completion of the online questionnaire.
6. Following the questionnaire and up till study end, only SADEs self-reported by the participants will be collected.
7. A subset of participants (20-30) who expressed an interest in participating in an interview will be invited for a 30 minute phone interview. Separate consent will be collected for the interview from all participants when approx. $\frac{1}{3}$ enrolment completed
8. HCP questionnaires will take place at each site after at least $\frac{1}{3}$ of that site's participants or at least $\frac{1}{3}$ of the total study participants (whichever is first for each site) have completed Visit 2.
9. The HCP focus groups will take place after the HCP questionnaires have been completed but may take place before all of the site's participants have received their study results.
10. The PCC focus group may be scheduled at any time after the HCP questionnaires have been issued.

4 STUDY VARIABLES

4.1 Safety Assessments - Adverse Events and Device Deficiency

Safety assessments include assessment of adverse events (AEs) and device deficiencies. The number and nature of these events will be recorded as safety variables.

The adverse event and device deficiency definitions are aligned to those in the international standard ISO 20916: 2019 for in vitro diagnostic medical devices, allowing for CVD IRT being a risk assessment tool rather than a diagnostic tool.

Terms and definitions relevant to safety assessments are provided in the table below.

| Term | Definition |
|------------------------------------|---|
| Adverse Event (AE) | Any untoward medical occurrence, inappropriate patient management decision, unintended disease or injury, or untoward clinical signs, whether or not related to the IVD or study procedures. |
| Serious Adverse Event (SAE) | AE that led to any of the following 
 a) death b) serious deterioration in the health of the participant as defined by one or more of the following 
 i) a life-threatening illness or injury, or ii) a permanent impairment of a body structure or a body function including chronic diseases, or iii) in-patient of prolonged hospitalisation, or iv) medical or surgical intervention to prevent life-threatening illness or injury or permanent impairment to a body structure or a body function c) foetal distress, foetal death or a congenital abnormality or birth |

| | |
|--|---|
| | defect including physical or mental impairment |
| Adverse Device Effect (ADE) | AE related to the use of an IVD. |
| Serious Adverse Device Effect (SADE) | ADE that has resulted in any of the consequences characteristic of a SAE |
| Unanticipated Serious Adverse Device Effect (USADE) | SADE which by its nature, incidence, severity or outcome has not been identified in this protocol. |
| Device deficiency | A device deficiency is an inadequacy of a medical device related to its identity, quality, durability, reliability, usability, safety, or performance, such as malfunction, misuse or use error or inaccurate results and inadequate labelling. |

Table 2: Terms and definitions relevant to safety assessments.

Adverse Event and device deficiency collection is detailed in the protocol (Section 9.2) and listed as reported.

4.2 Performance Outcomes

4.2.1 Primary Outcome

The primary endpoint will be measured both by operational success (report return rates), and feedback from HCPs, PCCs and patients via questionnaires, telephone interviews and focus groups.

4.2.2 Secondary Outcomes

The secondary endpoints will be measured as follows:

1. Changes in patient treatment based on risk scores at Visit 2.
2. Comparison of QRISK®2 and CVD IRT scores.
3. Feedback provided by HCP questionnaire as well as focus group(s) with HCPs and PCCs.
4. Participant questionnaires will be used to understand whether receiving the CVD IRT information had an impact on their health and wellbeing. Participant interviews will build on questionnaire responses to further understand impact on health and wellbeing.
5. Participant questionnaires will be used to understand whether they were engaged with CVD IRT information. Participant interviews will build on questionnaire responses to further understand the level of engagement.
6. Feedback provided by participant questionnaires and interviews as well as HCP questionnaires and focus group(s).

7. Percentage of results available and concordance with CVD IRT scores available from blood samples.
8. Comparison of PRS derived from DNA extracted from blood and saliva

4.2.3 Exploratory Outcomes

1. HCP questionnaires and focus groups and a PCC focus group will be used to understand how useful they consider the CVD IRT.
2. Further insights into future development of the genetic risk test tool will be gathered from all qualitative data sources, the participant questionnaires and interviews, the HCP questionnaires and focus groups, as well as the PCC focus group.

5 ANALYSIS SETS

5.1 Enrolled Participant Analysis Set

The Enrolled Participant Analysis Set will consist of all participants who have given consent and a blood sample taken.

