### 7.1. Patient Participants

Below is a table describing the study schedule for the patient participant, from consent through to online questionnaire and possible phone interview. The last three rows show the questionnaires and focus groups as planned for the HCPs and PCCs.

Procedures	Visit 1, Baseline	Visit 2, Results	Visit 3, Online Questionnaire	Visit 4, Phone Interview	
	Day 1	+ 5-12 weeks	+ 0-14 days after V2	up to 2 months after Visit 2	Study End
Informed consent 	X				
Demographics	X				
Inclusion/ Exclusion Criteria	X				
Blood sample 	X				
Saliva sample 	X				
QRISK®2 score 	X				
CVD IRT Results availability 		X			
Adverse Events 	X	X	X	X 	X 
Device deficiencies	X	X			
Participant Questionnaire	X		X		

Interview consent	X				
Participant Interview 				X	
HCP Questionnaire		X			X 
HCP Focus Group(s)					X 
NHS PCC Focus Group					X 

1. Signed, written informed consent obtained prior to any study specific procedure. Separate consent required for saliva samples.
2. 2x2.5ml samples for genetic analysis, the second sample as back-up in case of failure at any stage of processing.
3. A subset of participants (~100) at selected sites (1-3 sites depending on recruitment) will provide a 2ml saliva sample.
4. The QRISK score will be available some days after Visit 1. The IRT score will be available up to 12 weeks after the sample collection.
5. Related adverse events (ADEs) are to be collected from the provision of written informed consent up to the completion of the online questionnaire.
6. Following the questionnaire and up till study end, only SADEs self-reported by the participants will be collected.
7. A subset of participants (20-30) who expressed an interest in participating in an interview will be invited for a 30 minute phone interview. Separate consent will be collected for the interview from all participants when approx. ½ enrolment completed
8. HCP questionnaires will take place at each site after at least ½ of that site's participants or at least ½ of the total study participants (whichever is first for each site) have completed Visit 2.
9. The HCP focus groups will take place after the HCP questionnaires have been completed but may take place before all of the site's participants have received their study results.

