#### **7.1.5. Participant Consent**

The Principal Investigator (PI) will retain overall responsibility for the conduct of research at their site, including the taking of written informed consent of participants at their site. They will ensure that any person delegated responsibility to participate in the informed consent process is duly authorised, trained and competent to participate according to the ethically approved protocol, principles of Good Clinical Practice (GCP) and Declaration of Helsinki.

Physicians or practice nurses will take consent, as per delegation log.

Written informed consent will be obtained from the participant after they have been given adequate time and opportunity to discuss any study related questions with the health care team. Consent is anticipated to be provided during an appointment (in person) with the health care team, but may also be provided remotely, via telephone or video conference, and written consent will be obtained before any other study procedures (data and biosample collection) commence.

The staff member recording consent will be responsible for assessing the capacity of the interested participant to provide informed consent.

Patients will be informed that if they decline to participate in the study (without having to give a reason), that decision will not compromise their ongoing health care.

The sponsor will keep anonymised genetic data to support future research. If the participant does not wish to allow the sponsor to keep genetic data for future research, they will not be able to participate in the study.

The participant will remain free to withdraw at any time from the study without having to give a reason and without prejudicing their further management and will be provided with a contact point where they may obtain further information about the study. Where a participant is required to re-consent or new information is required to be provided to a participant it is the responsibility of the PI to ensure this is done in a timely manner.

The original signed consent form will be provided to the participant, and copies filed in the investigator site file (ISF) and participant medical notes if required by local practice.

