**Table 7: Event outcomes.**

## 9.2. Adverse Event Recording

Adverse event monitoring outlined in this protocol is reflective of the risk/benefit ratio of participating in the study to the patient. Intervention is minimal; an additional blood sample and saliva sample for a subgroup, the participant will receive a second CVD risk score in addition to the standard CVD QRISK®2 score, followed by an online questionnaire (and possible interview). All these activities are considered low risk.

To this end, the study will only collect adverse events considered related to study procedures or the risk assessment tool (CVD IRT). In addition, since all participants will provide a blood sample as part of standard practice (for QRISK®2), the study is requesting that study blood samples be collected using the same venepuncture. Therefore, mild events such as the following which are common when giving blood samples will not be collected for the study safety database:

- Pain
- Feeling faint
- Bruising
- Minor bleeding
- Haematoma
- Site infection

However, adverse events due to the process of blood sampling that are not common or are severe in nature will be collected. The WHO Best Practices for Injections and Related Procedures Toolkit can be referred to minimise adverse events.

From point of consent to collection of results at visit 2, all AEs considered related to the risk assessment tool or study procedures will be collected during visit 2 by the clinical team. At visit 3, the online questionnaire will be reviewed by the qualitative research team to identify related AEs and reported to the clinical team for documentation.

Similarly, during interviews, the qualitative research team (interviewer) will again identify related adverse events, but in this instance only those meeting the criteria of 'serious' will be collected. All SAEs will be forwarded to the clinical team for documentation.

Throughout the study, the participant will be invited to contact the study team at any time to discuss any concerns and issues raised by the study, and any related AEs identified will be collected as described above. Up to the point of online questionnaires, self-reported related adverse events will be collected and after the online questionnaires, self-reported related adverse events meeting the criteria of 'serious' will be collected until study end. Related SAEs should be followed to resolution if possible.

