7.1 Patient Disposition

Patient disposition information will be summarised for all enrolled Participants for the following disposition categories:

- Participants who were enrolled
- Participants who provided a sample
- Participants who completed a V3PartQ questionnaire
- Participants who completed a Visit 4 telephone interview

Participants who formally withdrew from the study

The primary reasons for terminating will be tabulated. The primary reason for early withdrawal from the study will also be tabulated.

In addition, the number and percentage of participants in each analysis set will be presented. All disposition data will be listed by patient.

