7.7 Safety Analyses

Safety assessments include treatment emergent adverse events and device deficiencies as per protocol.

All safety analyses will be performed by cohort and overall based on the Enrolled Participant Analysis Set.

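### Safety analyses rest on a set that requires a blood sample, although adverse events are collected from consent; consented but unsampled participants fall outside the safety counts and denominators

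*SAP*

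**What the plan says.** SAP 5.1 defines the set by two conditions: "The Enrolled Participant Analysis Set will consist of all participants who have given consent and a blood sample taken". SAP 7.7 then says: "All safety analyses will be performed by cohort and overall based on the Enrolled Participant Analysis Set".

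Collection starts earlier than membership of that set. Footnote 5 to the schedule of assessments (Protocol 7.1, Table 3, repeated in SAP 3.6) reads: "Related adverse events (ADEs) are to be collected from the provision of written informed consent up to the completion of the online questionnaire". Protocol 9.2 leaves out common mild events of a blood draw but adds that "adverse events due to the process of blood sampling that are not common or are severe in nature will be collected". Protocol 7.1.5 expects consent in person at an appointment, but says that it "may also be provided remotely, via telephone or video conference".

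SAP 4.1 adds a listing rule that names no analysis set: "Adverse Event and device deficiency collection is detailed in the protocol (Section 9.2) and listed as reported".

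SAP 7.1 has one disposition category for participants who were enrolled and a separate one for "Participants who provided a sample".

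For the report return rate, Protocol 10.3.1 and SAP 4.2.1 give no numerator, denominator or analysis set. SAP 7.5 refers to table layouts in appended files that were not available for this review.

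**The concern.** The period in which events are collected opens at consent, but the population in which they are analysed opens only when blood has been taken. Anyone in between is under safety observation and outside the safety analysis. The events most likely to occur there include a severe or unusual reaction to an attempted draw, which the protocol asks sites to report. Low numbers of events are expected (Protocol 9.2.1), so a single omitted event could be a visible part of the total.

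The same wording affects how the study accounts for its participants. If enrolled means consented and sampled, the disposition table cannot show how many people consented and gave no blood. If the Enrolled set also served as the return-rate base, participants from whom no blood was obtained would leave that rate too. The return rate is the operational part of the primary endpoint.

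**Working it through.** **Safety.** No arithmetic is needed; the rules can be followed in order.

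1. A participant gives written consent, possibly remotely before Visit 1 (Protocol 7.1.5 and 7.1.7.1). Related events are collected from this point.
2. Eligibility is confirmed, and the participant is added to The HEART Application and given an ID that goes on the enrolment log (Protocol 7.1.7.1). The text does not make this conditional on blood having been obtained.
3. The draw is attempted and yields no blood, or the participant withdraws first. Protocol 7.1.11 has a rule for withdrawals after samples were taken, which implies that withdrawal before sampling is possible.
4. If a severe or uncommon event accompanies the attempt, Protocol 9.2 requires it to be collected.
5. SAP 5.1 excludes this participant, so SAP 7.7 leaves the event out of the counts and the person out of the denominators.
6. SAP 4.1 may still bring the event into a listing.

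**Disposition.** Under the 5.1 meaning, the enrolled and sampled rows in SAP 7.1 hold the same people. Under the operational meaning in step 2 they can differ, but then one word has two meanings in the SAP.

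**Return rate.** The plan has no figure to reproduce: no target rate, no expected number unsampled and no stated base. The size below is conditional on the Enrolled set being the base.

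- N = 1000 registered participants (planned size, Protocol 10.1 and SAP 3.4).
- u = share of these with no blood sample: not in the documents, assumed 0.5% to 5%.
- r = return rate among sampled participants: not in the documents, assumed 90% to 99%.
- Rate on the sampled base = r. Rate on the registered base = r × (1 − u). Difference = r × u.

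With counts rounded to whole participants (sampled base, then registered base, then gap in points):

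| u | r = 90% | r = 95% | r = 99% |
|---|---|---|---|
| 0.5% | 896/995 = 90.05%; 89.60%; 0.45 | 945/995 = 94.97%; 94.50%; 0.47 | 985/995 = 98.99%; 98.50%; 0.49 |
| 1% | 891/990 = 90.00%; 89.10%; 0.90 | 940/990 = 94.95%; 94.00%; 0.95 | 980/990 = 98.99%; 98.00%; 0.99 |
| 2% | 882/980 = 90.00%; 88.20%; 1.80 | 931/980 = 95.00%; 93.10%; 1.90 | 970/980 = 98.98%; 97.00%; 1.98 |
| 5% | 855/950 = 90.00%; 85.50%; 4.50 | 902/950 = 94.95%; 90.20%; 4.75 | 940/950 = 98.95%; 94.00%; 4.95 |

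For scale, at r = 95% the Wilson 95% intervals on the two bases are 93.4–96.2% and 92.9–95.8% when u = 0.5%, which largely overlap. When u = 5% they are 93.4–96.2% and 88.2–91.9%, which do not overlap.

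**The case against.** On safety, the other side can say that the group is probably small. Remote consent is an option and not the expected route, only related events are collected, common mild events of the draw are excluded, and few events are expected. The sponsor also collects events centrally (Protocol 9.4.4), and the SAP 4.1 listing is not restricted to any set. This limits the likely size and means that an event need not disappear from reporting. It does not supply the missing counts and denominators, because SAP 7.7 covers all safety analyses.

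On disposition, enrolled in SAP 7.1 may mean operational enrolment, in which case unsampled participants are already visible. That is possible, but the SAP does not say so.

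On the return rate the objection is stronger. A reader might infer that SAP 5.1 removes unsampled participants from the return-rate base and so inflates the primary result. The documents do not establish this, because they name no base and SAP 5.1 assigns the Enrolled set no use. The Enrolled set is a plausible base, since the CVD IRT set in SAP 5.3 requires a valid report and would give 100% by construction, but that is inference. A reader might also infer that laboratory and transport failures are hidden. They are not: the reasons Protocol 7.1.7.1 gives for a missing score (loss in transit, inadequate DNA, no PRS) all arise after blood is taken, so those participants stay in the set. Finally, standard-care and study blood come from one venepuncture, so a failed draw is not clearly a failure of adding the genetic test.

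A further fair objection is that using everyone who consented as the return-rate base would go too far. Eligibility is confirmed after consent, so people found ineligible would count as failures to return a report.

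**Conclusion.** The safety point holds on the text alone: SAP 5.1 and 7.7 together leave in-scope events out of the safety counts, and the people concerned out of the denominators, whenever consent was given and no blood was obtained. How often this will happen cannot be derived from the documents, and it may be rare. The two disposition categories in SAP 7.1 need reconciling with 5.1.

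For the return rate, the supportable conclusion is that the available text does not specify the base. Only if the Enrolled set is used does the choice matter, by about r × u: about 0.5 points at u = 0.5%, rising to 4.5–5.0 points at u = 5%, with r assumed between 90% and 99%. Both inputs are assumptions. The available text sets no threshold for the return rate, so no stated decision turns on the difference.

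**What to change.** - **SAP 7.7:** base the safety analyses on all participants who gave written informed consent, to match the start of event collection.
- **SAP 5.1 and 7.1:** give enrolled one meaning, and show consented, registered and sampled participants as separate counts, so that those who consented and gave no blood are visible.
- **Dependent sets:** the sets in SAP 5.2 to 5.7 are built on the Enrolled set. If 5.1 is widened, keep the sample requirement explicitly where the analysis needs it, in particular for the paired saliva–blood comparison in SAP 5.7. A separate safety set would avoid this knock-on effect.
- **Return rate:** state the numerator and denominator in the SAP. Report the rate among consented, eligible participants registered in The HEART Application, with the rate among sampled participants as supportive.

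The cost is SAP wording, including a check of the dependent sets. No new data collection is needed. The return rate may come out slightly less favourable.
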